4.5 Justification for Exclusion of Women, Minorities, and Children (Special Populations)

Exclusion of Children:

This Pilot study is being specifically undertaken in a population at risk for cognitive decline, thus our recruitment of people 55 years or older.

Other Exclusionary Criteria:

- Participants with creatinine clearance less than 60 ml/min will be excluded due to investigating the effects on metabolites relevant to neuronal health. We do not want interference from alterations in metabolites due to renal insufficiency.
- Diabetics will be excluded because they are likely to have an increase in circulating ketones and a lowering of blood glucose while on sGLT2 inhibitors. We want to study if this will occur in non-diabetic subjects in the specified age group of interest.
- BMI > 35 kg/m² are excluded due to production and use of ketone bodies which are impaired in obese individuals (Vice E et al. Metabolism 2005).

Exclusion of Non-English-Speaking Subjects:

- The NIA Clinical Research Unit is located in Baltimore, Maryland. We do not have ready access to interpreters of different languages.

4.6 Justification for Inclusion of Other Vulnerable Subjects (NIH Staff)

We intend to include NIH staff (to include NIH contractors and special volunteers, guest researchers and trainees) in this study. The staff may through standard recruitment efforts screen for the study. No direct solicitation of employees/staff will take place. Participation will be voluntary and neither participation nor refusal to participate will have an effect either beneficial or adverse, on the participant's employment or position at NIH. *Informed Consent Process* and confidentiality maintained as per Section 13.3, *Subject Confidentiality*, Section 14, discussed below. All staff interested in enrolling in this study will be given a copy of the *NIH Information Sheet on Staff Research Participation* (Appendix B).

For NIH employees:

- Neither participation nor refusal to participate will have an effect, either beneficial or adverse, on the participant's employment or work situation.
- The NIH information sheet regarding NIH employee research participation will be distributed to all potential subjects who are NIH employees.
- The employee subject's privacy and confidentiality will be preserved in accordance with NIH policies, which define the scope and limitations of the protections.
- Subjects that are employees/staff will be consented in the usual manner. The inclusion of employees or staff is not anticipated to affect the research outcome; therefore, if the subject is a co-worker (including a supervisor, subordinate or coworker) the subject may be consented by another co-worker and/or

subordinate. The study PI will not be involved in the consenting of employees or staff.

- Remuneration for employees/staff will follow the leave policy for *NIH Employees Participating in NIH Medical Studies (Appendix B)*.

5 Study Schedule

The study is expected to be completed by the end of 2021.

5.1 Phone Screening (Pre- Study)

Initially, potential participants are screened by the NIA recruiter using a standardized telephone screen. The PI, CRC or research nurses will review the telephone screen for completeness and contact the participant if there are any questions.

5.2 Screening Visit (Visit 0)

Participants who are eligible following the phone screen will come to the NIA Clinical Research Unit for about 1.5 hours. The screening visit will include the following tests and procedures:

- a. Informed Consent.
- b. Height/Weight and Vital Signs (blood pressure, pulse, temperature, respirations and pulse oximetry).
- c. Fasting Blood Tests (fasting at least 8 hours): fasting glucose, Complete Blood Count (CBC), Liver and Kidney function, Thyroid function, Serum Chemistries, HbA1c, cortisol level, HIV, Hepatitis B surface antigen, and Hepatitis C antibodies. (If a participant has a positive Hepatitis C test, the MedStar Harbor Hospital Lab will automatically have further testing on the blood sample for HCV RNA quantitative). Positive HIV and Hepatitis testing results are reported to the Maryland Department of Health and the screened participant will receive counseling by the study medical staff.
- d. Medical History and Physical Exam.
- e. A snack or meal will be provided.

Based on the information collected, study eligibility is established, and the participant is invited to come for Visit 1. For eligible participants, a copy of their laboratory results will be provided prior to or at their Baseline Visit. If ineligible, a letter is sent within 1-3 weeks confirming ineligibility along with the results of their laboratory testing.

5.3 Visit 1 Baseline – No study medication given

At Visit 1, the enrolled participant will come to the NIA Clinical Research Unit for a two-day visit, lasting approximately 34 hours. The following procedures will be done:

- a. Height/weight, orthostatic blood pressure measurements, pulse, temperature, respirations and pulse oximetry.
- b. I.V. placement for fasting blood tests (fasting for at least 8 hours) including CMP, lipids, insulin and other hormones, and exosomes. Followed by blood sampling every 1.5-hours x 2, then q 1-hour x 1, then q 1.5-hours x 8, then q 2-hours x 4, then q 1.5-hours x 2, then q 1-hour x 1, then q 1.5-hours x 4 (completes 34-hours). This frequent sampling will include β -hydroxybutrate (β -OHB), acetoacetate, fatty and amino acids, glucagon, insulin and glucose levels. On Day 2, exosomes will be repeated and oxysterols and lipidomics will be drawn.
- c. Placement of a continuous glucose monitor (CGM) used to collect data for up to 14 days, worn by the participant until they return for Visit 2.
- d. 34-hour urine collection for creatinine clearance, C-peptide, and other hormones.
- e. Brain MRS and limited brain MRI for voxel placement, required anatomical studies and resting functional connectivity will be conducted.
- f. All meals will be provided. The meals on visits 1, 2 and 3 will be pre-selected by the participant. Food intake will aim to be uniform at all visits and at consistent times. Participants will be asked to record the time and items they eat on a Food Diary (Appendix C). They will also be instructed to hydrate. This includes drinking 8 ounces of water every 4 hours except when asleep.
- g. On the evening of Day 1, the participants will be given an activity monitor and will be instructed to walk 2,000 steps before bedtime.
- h. Discharge instructions will be given (Appendix D). They will wear the CGM and be asked to complete an Intake Diary (Appendix E) to record consuming anything other than water to assist with the CGM data collection.

5.4 Visit 2 occurs 13 +/- 2 days from Visit 1

Initiation of sGLT2 inhibitor (empagliflozin)

At Visit 2, the enrolled participant will come to the NIA Clinical Research Unit for a two-day visit, lasting approximately 34 hours. This visit will be the same as Visit 1, except the participant will receive a daily dose of empagliflozin (Jardiance).

The following procedures will be done:

- a. Height/weight, orthostatic blood pressure measurements, pulse, temperature, respirations and pulse oximetry.
- b. I.V. placement for fasting blood tests (fasting for at least 8 hours) including CMP, CBC, lipids, insulin and other hormones, and exosomes. The study drug empagliflozin (Jardiance) will be administered at approximately 8:00 a.m. followed by blood sampling every 1.5 hours x 2, then q 1-hour x 1, then q 1.5-hour x 8, then q 2-hours x 4, then q 1.5-hours x 2, then q 1-hour x 1, then q 1.5-hours x 4 (completes 34-hours). This frequent sampling will include β -hydroxybutrate (β -OHB), acetoacetate, fatty and amino acids, glucagon, insulin and glucose levels. On Day 2, exosomes will be repeated and oxysterols and lipidomics will be drawn.
- c. Placement of a continuous glucose monitor (CGM) used to collect data for up to 14 days, worn by the participant until they return for Visit 3.
- d. 34-hour urine collection for creatinine clearance, C-peptide, and other hormones.

- e. Breakfast will be given within 30 minutes of dosing.
- f. All meals will be provided. They will aim to be consistent items and times as what was consumed on Visit 1. Participants will be asked to record the time and items they eat on a Food Diary (Appendix C). They will also be instructed to hydrate. This includes drinking 8 ounces of water every 4 hours except when asleep.
- g. On the evening of Day 1, the participants will be given an activity monitor and will be instructed to walk 2,000 steps before bedtime. They will be instructed when they are discharged to continue to walk 2,000 steps every evening while wearing the activity monitor. This will occur during the time they are taking the study medication at home.
- h. Day 2: Participants will receive empagliflozin (Jardiance) 25 mg followed by breakfast within 30 minutes.
- i. Brain MRS and limited brain MRI for voxel placement, required anatomical studies and resting functional connectivity will be conducted.
- j. Following the final blood draw, participants will be sent home and instructed on self-administration of a daily morning dose of empagliflozin (Jardiance) 25 mg and will wear the CGM until returning for Visit 3.
- k. Discharge instructions will be given (Appendix F). They will wear the CGM and be asked to complete an Intake Diary (Appendix E) to record consuming anything other than water to assist with the CGM data collection.
- l. A staff member will phone participants daily to assure they are taking the study medication and to assess for any symptoms. We will also remind them about the importance to hydrate, as stated above (f).

5.5 Visit 3 occurs 13 +/- 2 days from Visit 2

At Visit 3, the enrolled participant will come to the NIA Clinical Research Unit for a two-day visit, lasting approximately 34 hours. The following procedures will be done:

- a. Height/weight, orthostatic blood pressure measurements, pulse, temperature, respirations and pulse oximetry.
- b. I.V. placement for fasting blood tests (fasting for at least 8 hours) including CMP, lipids, insulin and other hormones. The study drug empagliflozin (Jardiance) will be administered at approximately 8:00 a.m. followed by blood sampling the same as visits 1 and 2. Breakfast will be given within 30 minutes of dosing.
- c. Placement of a continuous glucose monitor (CGM) used to collect data for up to 14 days, worn by the participant until the end of Visit 3.
- d. 34-hour urine collection for creatinine clearance, C-peptide, and other hormones.
- e. All meals will be provided. They will aim to be consistent items and times as what was consumed on Visits 1 and 2. Participants will be also be instructed to hydrate. This includes drinking 8 ounces of water every 4 hours except when asleep.
- f. On the evening of Day 1, the participants will be given an activity monitor and will be instructed to walk 2,000 steps before bedtime.
- g. Day 2: Participants will receive empagliflozin (Jardiance) 25 mg followed by breakfast within 30 minutes.
- h. Brain MRS and limited brain MRI for voxel placement, required anatomical studies and resting functional connectivity will be conducted.

- i. Following the final blood draw, participants will have completed the study. They will no longer take the study medication or wear the CGM.
- j. Discharge instructions will be given (Appendix G).

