6.1 Clinical Evaluations and MRI/MRS

Medical History and General Physical Examination

Participants receive a standardized physical exam and medical evaluation to include vital signs. Review of concomitant medications. This evaluation is required for study participation.

Body Measurements

Height and weight will be measured. These measurements are required for study participation.

Vital signs/Orthostatic blood pressures

This will be done to monitor for any problems of potential hypotension or dehydration.

Blood samples

Blood work for clinical chemistry, hematology, lipids, oxysterols, lipidomics, and exosomes will be done along with frequent blood sampling for hormones and ketones. An intravenous catheter will be placed for frequent sampling.

Safety Labs

Participants will have a fasting CMP/Lipid Panel on Day 1 of Visits 1, 2 and 3. On Visits 2 and 3 they will also have a CBC to monitor hemoglobin and hematocrit levels. Should a participant have a decrease of greater than 10% from the screening visit, the number of frequent blood draws would be decreased to every 2 hours. Therefore, the amount of blood taken on that visit would be approximately 130 ml (8.8 tablespoons).

Continuous Glucose Monitor (CGM)

The *Free Style Libre Pro* Continuous Glucose Monitor (CGM) device will be placed to measure interstitial glucose concentrations on Visits 1, 2 and 3. At the end of Visits 1 and 2 participants will wear the device until they return for Visits 2 and 3. The device will be removed at the end of Visit 3. The monitor consists of a small sensor that is inserted with a small needle and measures glucose levels just underneath the skin on the abdomen or the arm. The monitor will be inserted by the staff and the participant will be trained on wearing the device and who to call with questions or problems. A transmitter sends data wirelessly to the receiver. Once completed, data will be downloaded from the device to secure NIA servers.

Activity Monitor

On the evening of Day 1, participants will be given an activity monitor to wear on their wrist and will be instructed to walk approximately 2,000 steps. This will be done to try and keep activity levels similar in the 20 participants.

Study Medication

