6.2 Laboratory Evaluations

6.2.1 Laboratory Samples

Blood Samples

Fasting blood samples are used to measure levels of chemicals, proteins, enzymes, inflammatory markers, markers of oxidative stress, lipids, minerals, hormones,

ketones and blood cells. Blood samples may include but are not limited to the following list.

Screen Visit: Fasting for at least 10 hours

- Comprehensive Chemistry Panel, ALT, AST, Alkaline Phosphatase, Total Bilirubin, thyroid panel
- Complete Blood Count (CBC) with Differential and Related Variables
- Hepatitis B surface antigen
- Hepatitis C antibody total
- HIV 1-2 antibody screen
- HbA1C
- Cortisol level
- Urinalysis

Visit 1

- Fasting Comprehensive Chemistry Panel, Lipids, oxysterols, lipidomics
- Exosomes (e.g., beta amyloid)
- β -hydroxybutrate (β -OHB), acetoacetate, fatty acids and amino acids
- Glucose, insulin and glucagon
- Urinalysis

Visits 2 and 3:

- Same as Visit 1, except CBC will be done for safety

Urine Sample

A 24-hour urine sample will be collected for creatinine clearance, C-Peptide and other hormones on Visits 1, 2 and 3.

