Risks of Study Medication empagliflozin (Jardiance): The most common adverse reactions associated with administration of empagliflozin are dehydration, dizziness, lightheadedness, weakness, yeast and urinary tract infections. To decrease these risks, participants will be encouraged to hydrate and to maintain good hygiene. Other side effects may include low blood sugar, nausea, and upper respiratory tract infections. There also may be other side effects that we cannot predict, including hypersensitivity reaction. Rarely, sudden episodes of kidney injury may occur. Also, the Food and Drug Administration (FDA) has issued a warning about rare occurrences of a serious infection of the genital area (necrotizing fasciitis of the perineum) associated with sGLT2 inhibitors. Both of these have only been known in people who have diabetes. We will monitor for any symptoms during our daily calls to the participant while they are on study medication. This will include questioning any symptoms of tenderness, redness,

or swelling of the genitals or the area from the genitals back to the rectum. We will also monitor for fever or general feeling of being unwell.

Risks of Continuous Glucose Monitor (CGM): Potential risks include a slight skin irritation from the adhesive.

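### As scheduled, the Visit 2 creatinine clearance pairs a pre-dose serum creatinine with urine collected during dosing, so it would understate a mild or moderate acute fall in filtration

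*Combined protocol and SAP*

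**What the plan says.** Sections 5.3, 5.4 and 5.5 (item d of each) call for a "34-hour urine collection for creatinine clearance, C-peptide, and other hormones", and the section 6 table repeats the 34 hours. Section 6.2.1 differs: "A 24-hour urine sample will be collected for creatinine clearance, C-Peptide and other hormones on Visits 1, 2 and 3".

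Serum creatinine is scheduled only as part of the chemistry panel. Section 6.1 (Safety Labs) states: "Participants will have a fasting CMP/Lipid Panel on Day 1 of Visits 1, 2 and 3". Section 5.4 item b lists these fasting bloods first and then continues: "The study drug empagliflozin (Jardiance) will be administered at approximately 8:00 a.m. followed by blood sampling every 1.5 hours x 2". The Visit 2 panel is therefore pre-dose.

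For the later draws, item b states: "This frequent sampling will include β -hydroxybutrate (β -OHB), acetoacetate, fatty and amino acids, glucagon, insulin and glucose levels". It adds: "On Day 2, exosomes will be repeated and oxysterols and lipidomics will be drawn". Creatinine is in neither list. The second dose is given on the morning of Day 2, inside the collection period.

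The documents give no clearance formula, do not say which serum value enters it, and do not say when the collection starts relative to the dose.

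**The concern.** A clearance calculation assumes that the serum and urine values describe the same state of the kidney. When filtration falls, serum creatinine rises until urinary output is back at the production rate. Urinary creatinine over a day or more then looks close to normal, and dividing it by the old, lower serum value gives a clearance that also looks close to normal.

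Only Visit 2 mixes the two states. Visit 1 is off drug throughout. At Visit 3 the serum is drawn after about two weeks of dosing.

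At stake is the one estimate of kidney function that covers the first two doses, taken just before 13 +/- 2 days of home dosing. Tolerability in this age group is a secondary objective (section 2.2), and section 7.1 states of the drug: "Rarely, sudden episodes of kidney injury may occur".

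**Working it through.** **Plan's own figure.** The listed sampling intervals sum to 1.5x2 + 1x1 + 1.5x8 + 2x4 + 1.5x2 + 1x1 + 1.5x4 = 34.0 h. That is 2+1+8+4+2+1+4 = 22 draws after baseline, including draws at 11.5, 13, 16, 18, 24 and 34 h. The stated 34 hours is reproduced.

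**Inputs**
- Collection length T: 34 h (sections 5.3-5.5, section 6 table) or 24 h (section 6.2.1).
- Baseline clearance GFR: 60-120 ml/min. Only the floor of 60 is in the documents (section 4.4); the upper end is assumed.
- Creatinine distribution volume V: 30-50 L (assumed).
- Also assumed: constant production, an immediate and lasting fall f in filtration at the dose, no change in tubular secretion, and collection starting at the dose.

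**Formulas**
- Rate constant per hour: k = 0.06 x GFR x (1 - f) / V.
- Serum creatinine relative to baseline at time t: R(t) = [1 - f exp(-kt)] / (1 - f).
- Urinary creatinine over T relative to production: E = 1 - f [1 - exp(-kT)] / (kT).
- Apparent fall with the pre-dose serum value: 1 - E.
- Apparent fall with a serum value drawn at time s: 1 - E / R(s).

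**Worked case: f = 0.20, GFR 100, V 42, T = 34**
- k = 0.06 x 100 x 0.8 / 42 = 0.1143; kT = 3.886; exp(-3.886) = 0.0205.
- Pre-dose serum: 0.2 x 0.9795 / 3.886 = 0.050, so a 20% fall reads as 5.0%.
- Serum at 16 h: exp(-1.829) = 0.1606; R = (1 - 0.0321) / 0.8 = 1.210; 1 - 0.9496 / 1.210 = 0.215, so it reads as 21.5%.

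**Ends of the range: f = 0.20, T = 34**
- GFR 60, V 50: k = 0.0576, kT = 1.958; 0.2 x (1 - 0.1411) / 1.958 = 8.8%.
- GFR 120, V 30: k = 0.192, kT = 6.528; 0.2 x (1 - 0.0015) / 6.528 = 3.1%.

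**Apparent fall over the whole assumed range (same formulas)**

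| True fall | 34 h, pre-dose serum | 34 h, serum at 16 or 18 h | 24 h, pre-dose serum | 24 h, serum at 11.5 h |
|---|---|---|---|---|
| 10% | 1.4-4.0% | 10.5-11.2% | 1.9-5.1% | 10.3-11.0% |
| 20% | 3.1-8.8% | 20.7-22.1% | 4.3-10.8% | 20.5-21.7% |
| 30% | 5.2-14.4% | 30.8-32.8% | 7.3-17.4% | 30.5-32.2% |
| 50% | 12.0-28.8% | 50.5-53.3% | 16.4-33.5% | 50.3-52.2% |
| 70% | 26.1-49.6% | 70.0-72.6% | 33.3-54.6% | 70.0-71.2% |
| 90% | 61.5-79.8% | 89.8-90.7% | 68.4-82.7% | 89.9-90.0% |

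Over 34 h, more than half of any 10-30% fall is hidden across the whole range (52-86%). For a 90% fall only 11-32% is hidden. A serum value near mid-collection recovers the true fall closely for either length.

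**The case against.** **The plan does not force this calculation.** A reader might infer that the Visit 2 clearance can be computed in no other way. The documents do not go that far. Section 6.2.1 leaves the analyte list open ("Blood samples may include but are not limited to the following list"), samples are banked (section 6.2.2), and no serum value is named for the formula. A post-dose creatinine might still be measured. What stands is that none is scheduled, so following the plan as written produces the mismatch.

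**Length and start are unsettled.** The 34 and 24 hours conflict, and the shorter collection hides less. The start relative to the dose is inferred. In this model, though, the shortfall in urinary creatinine is largest just after dosing (f exp(-kt)) and zero before it. Moving a collection of the same length some hours earlier or later would therefore not reduce the masking.

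**Severe injury would still be seen.** A reader might infer that any kidney injury would be missed at Visit 2. The table does not support this for falls of 70-90%. A sustained fall of any size would also reach the Visit 3 panel and clearance. Orthostatic pressures, urinalysis and daily symptom calls continue, although none of them measures filtration.

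**The stakes are limited.** Section 1.2 applies its acute and chronic aim to ketones, metabolites and hormones, not to the kidney. Section 7.1 adds that the kidney injury has been known only in people with diabetes, whom this study excludes. Clearance is neither a named endpoint nor a safety trigger, and no comparison of it between visits is specified. All of this stands. It lowers the priority of the point but leaves the measurement error in place.

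**Conclusion.** The point holds for the schedule as written and for mild to moderate acute falls at Visit 2. The listed serum creatinine is pre-dose, the urine spans two doses, and the resulting clearance is biased towards no change. A true 20% fall would read as about 3-9% over 34 h or 4-11% over 24 h, and a 50% fall as about 12-29% or 16-34%. These sizes rest on the assumed clearance and volume ranges, an immediate and lasting fall, and a collection starting at the dose. The direction of the bias needs only that urine is collected after a fall that the serum sample precedes.

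The documents do not support saying that a planned analysis is invalidated, since none uses clearance. The gap is confined to the acute Visit 2 estimate. It is worth correcting because a value that falsely suggests stable function could be taken as evidence of tolerability, and the correction is cheap.

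**What to change.** 1. Reconcile the 34-hour collection (sections 5.3-5.5 and the section 6 table) with the 24-hour sample (section 6.2.1), and state the start time relative to dosing.
2. Add creatinine to the existing draw nearest the midpoint of the reconciled collection. Counting from the dose, that is the 16 h or 18 h draw for 34 hours, or the 11.5 h draw (nearest 12 h) for 24 hours. Do this at all three visits so that clearance is computed in the same way each time.
3. State the clearance formula and that it uses the mid-collection serum value.

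Optional: add a creatinine at the end of the collection, and report the ratios of Visit 2 and Visit 3 clearance to Visit 1 under tolerability. An end value averaged with the pre-dose value is a weaker substitute for the mid-collection one: over 34 h a 20% fall then reads as 13.8-17.6%.

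Cost: one assay per visit, 3 x 20 = 60 in total, on blood already drawn, plus the wording changes. No extra needle stick is needed, and no dose, clinical threshold or management rule is proposed.
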